### 6.3 Exclusion Criteria

1. Multiple Sclerosis disease duration > 25 years
2. Optic neuritis in prior 6 months
3. Known optic neuritis in involved eye  $\geq 10$  years ago
4. Major ophthalmologic disease/Concomitant ophthalmologic disorders (e.g. diabetes, macular degeneration, glaucoma, severe myopia, etc.).
5. Myopia > -7 Diopters (severe myopia)
6. Disc hemorrhages in qualifying eye
7. No light perception in qualifying eye
8. Simultaneous bilateral optic neuritis
9. Cotton wool spots in qualifying eye
10. Macular star in qualifying eye
11. History of significant cardiac conduction block
12. History of cancer (except non-melanoma skin cancer)
13. Suicidal ideation or behavior in 6 months prior to baseline
14. Pregnancy, breastfeeding, or planning to become pregnant

15. Included with other study protocol simultaneously without prior approval
16. Concomitant or prior use of any other putative remyelinating therapy as determined by investigator, including but not limited to Clemastine, Duavée, and Tamoxifen.
17. Serum creatinine > 1.5mg/dL; AST, ALT, or alkaline phosphatase > 2 times the upper limit of normal
18. History of drug or alcohol abuse within the past year
19. Untreated B12 deficiency (as determined by B12 serological assessments and metabolites including methylmalonic acid [MMA] and homocysteine) or untreated hypothyroidism
20. Clinically significant cardiac, metabolic, hematologic, hepatic, immunologic, urologic, endocrinologic, neurologic, pulmonary, psychiatric, dermatologic, allergic, renal or other major diseases that in the PI's judgement may affect interpretation of study results or patient safety.
21. History of or presence of clinically significant medical illness or laboratory abnormality that, in the opinion of the investigator would preclude participation in the study.
22. Patients whose lack of mobility exposes them to an increased risk of venous thromboembolism
23. Patients with undiagnosed uterine bleeding
24. Patients with unknown, suspected or past history of breast cancer
25. Patients with known or suspected estrogen-dependent neoplasia
26. Patients with active or a past history of venous thromboembolism
27. Patients with active or a past history of arterial thromboembolism
28. Patients with known protein C, protein S, or antithrombin deficiency or other known thrombophilic disorders
29. Patients with hypersensitivity (angioedema, anaphylaxis) to estrogens, bazedoxifene, or any ingredients
30. Patients with known hepatic impairment or disease

## 7 CONCURRENT MEDICATIONS

All subjects should be maintained on the same medications throughout the entire study period, as medically feasible, with no introduction of new chronic therapies.

### 7.1 Allowed Medications and Treatments

Standard therapy for MS is allowed except for treatments noted in the exclusion criteria described above.

## 8 STUDY TREATMENTS

### 8.1 Method of Assigning Subjects to Treatment Groups

Up to 50 eligible patients will be randomly assigned to 'Early' or 'Delayed Start' treatment groups in a 1:1 ratio using a SAS-based computer-generated randomization scheme developed by the study data management provider. The CTSI statistician advising the PI will complete a randomization worksheet.

## 8.2 Blinding

Due to the objectives of the study, the identity of test and control treatments will not be known to investigators, research staff, or patients. The following study procedures will be in place to ensure double-blind administration of study treatments.

- Access to the randomization code will be strictly controlled.
- The CTSI statistician advising the PI will perform the randomization/blinding chart and provide this to the Compounding Pharmacy. They will perform interim safety analysis without unblinding the study, and will only unblind the study to the investigators at the end of study.
- Packaging and labeling of test and control treatments will be identical to maintain the blind.
- Packaging and labeling will be done by pharmacy personnel who are not involved in analysis of study data.

The study blind will be broken on completion of the clinical study and after the study database has been locked. The investigators will be given the randomization worksheet from the CTSI statistician after the last participant has completed their study.

During the study, the blind may be broken **only** in emergencies when knowledge of the patient's treatment group is necessary for further patient management. When possible, the Investigator should discuss the emergency with [name] prior to unblinding.

## 8.3 Formulation of Test and Control Products

### 8.3.1 Formulation of Test Product

BZA is a third-generation selective estrogen receptor modulator (SERM). It is an immediate release, film-coated capsule shaped tablet. Tablets contain 20 mg of bazedoxifene expressed as free base. The tablets are supplied from Pfizer in blister packaging (commercially available Conbriza) and delivered to the compounding pharmacy unopened.

For blinding, it will be encapsulated in a gelatin capsule and fill remaining space with microcrystalline cellulose, by Koshland Compounding Pharmacy ([name]) at:

Koshland Pharm  
[name]  
[name]  
(p) [contact]  
(f) [contact]

Table 1: Formulation and Measured pH of BZA and Placebo

	2x (BZA, 20 mg)	Placebo
Active Ingredient, mg/mL	Bazedoxifene acetate	
Other ingredient, mg/mL	Lactose, microcrystalline cellulose, pre-gelatinised starch	Microcrystalline cellulose

	(maize), sodium starch glycolate, sodium lauryl sulfate, colloidal anhydrous silica, magnesium stearate, ascorbic acid, hypromellose, titanium dioxide (E171) and macrogol 400.	
--	---	--

### 8.3.2 Formulation of Control Product

Placebo is: Microcrystalline cellulose, encapsulated into a gelatin capsule, taken daily.

### 8.3.3 Packaging and Labeling

Both the drug and the placebo will be single use daily capsules (2/day) packaged into monthly bottles. Each carton (kit) of study drug will be labeled with the required FDA warning statement, the protocol number, a treatment number, the name of the sponsors, and directions for patient use and storage.

## 8.4 Supply of Study Drug at the Site

The Sponsor ([name]) will ship Study Drug to the investigational pharmacy. The initial study drug shipment will be shipped after site activation (i.e., all required regulatory documentation has been received by the Sponsor and a contract has been executed). Subsequent study drug shipments will be made as needed, per pace of enrollment and drug expiration requirements.

The randomization and blinding chart will be provided by CTSI statistician to the pharmacy personnel. Koshland Compounding Pharmacy will then ship the study drug to the PI, and the research team (PI or research coordinator) will give the package to participants at research visits (quantity of study drug determined by expiry of investigational product batch).

### 8.4.1 Dosage/Dosage Regimen

The medication (BZA or placebo) will be taken once daily, in the morning, for the duration of the study (stage 1 = 3 months, stage 2 = 3 months).

### 8.4.2 Dispensing

The Koshland Compounding pharmacy will ship the drugs to study personnel, who will then give the samples to the study participants at each research visit. Should the available batch of study drug carry an expiration fewer than 3 months from the time of dispensing, study staff may provide a 1-2month supply at the time of the visit and then re-supply with newer stock via mail or in-person delivery.

### 8.4.3 Administration Instructions

Patients will take 2 capsules orally once a day.

## 8.5 Supply of Study Drug at the Site

Study personnel will receive the Study Drug/placebo shipment from the Koshland Compounding Pharmacy and maintain it under locked conditions in the Sandler Neurosciences Center. Subjects will be randomized and provided the study drug on the same day.

### **8.5.1 Storage**

Study drug should be stored by the study site at controlled room temperature, 15 to 30°C (59 to 86°F). Subjects will be instructed to store the medication in bottles at room temperature according to the instructions outlined on the Drug Administration Instructions.

### **8.6 Study Drug Accountability**

An accurate and current accounting of the dispensing and return of study drug for each subject will be maintained on an ongoing basis by a member of the study site staff. The number of study drug dispensed and returned by the subject will be recorded on the Investigational Drug Accountability Record. The study monitor will verify these documents throughout the course of the study.

### **8.7 Measures of Treatment Compliance**

Subjects will be asked to keep a patient diary noting the day and date they take their study drug and any adverse events. They will be asked to bring their patient diary to each study visit along with all used and unused study drug containers.

## **9 STUDY PROCEDURES AND GUIDELINES**

A Schedule of Events representing the required testing procedures to be performed for the duration of the study is diagrammed in Appendix 1.

Prior to conducting any study-related activities, written informed consent and the Health Insurance Portability and Accountability Act (HIPAA) authorization must be signed and dated by the subject. If appropriate, assent must also be obtained prior to conducting any study-related activities.

### **9.1 Clinical Assessments**

#### **9.1.1 Concomitant Medications**

All concomitant medication and concurrent therapies will be documented at Baseline/Screening and at Study visits, and at early termination when applicable. Dose, route, unit frequency of administration, and indication for administration and dates of medication will be captured.

#### **9.1.2 Demographics**

Demographic information (date of birth, gender, race) will be recorded at Screening.

#### **9.1.3 Medical History**

Relevant medical history, including history of current disease, other pertinent respiratory history, and information regarding underlying diseases will be recorded at Screening.

#### **9.1.4 Physical Examination**

A complete physical examination will be performed by either the investigator or a sub-investigator who is a physician at the Screening Visit. Qualified staff (MD, NP, RN, and PA) may complete the abbreviated physical exam at all other visits. New abnormal physical exam findings must be documented and will be followed by a physician or other qualified staff at the next scheduled visit.

### 9.1.5 Vital Signs

Body temperature, blood pressure, pulse and respirations will be performed after resting for 5 minutes at all Study Visits.

### 9.1.6 Other Clinical Procedures

#### Timed Walking Assessments:

**T25W:** The Timed 25-foot Walk will be assessed according to the schedule in Appendix-1. The Timed Walk is an objective quantitative test of neurological function, and is one of three components of the Multiple Sclerosis Functional Composite (MSFC), a composite measure assessing upper extremity function, ambulation and cognitive function (Fisher et al. 1999). The Timed Walk is an ambulation measurement: a walk of 25 feet (7.62 meters): time taken in seconds. The Timed Walk test will be administered either by the Independent EDSS Rater or by another qualified individual not involved in the treatment of the patients.

**6-minute walking distance:** The distance subjects can walk in 6 minutes will be assessed on 3 separate occasions as indicated in Appendix-1. The evaluating physician will use a measured hallway to assess the distance subject can walk at safe comfortable speed over a 6-minute period.

**Timed up and go (TUG):** The TUG test is a valuable measure of subject's gait and postural stability which will be administered according to the schedule in Appendix-1. The test requires that subjects start seated in an arm chair, stand up, walk 3 meters to a designated line, then return to their starting seated position. As a safety precaution, the trained evaluator should maintain a close distance to the subject throughout the test.

#### Symbol Digit Modalities Test (SDMT):

The SDMT will be assessed according to the schedule in Appendix-1 (study coordinator to administer). The SDMT is a sensitive and specific test to assess processing speed and working memory which are typically affected domains in cognitively impaired MS patients. During the administration of the SDMT, only the examiner and the patient should be in the testing room. The examiner can be the study coordinator, independent EDSS Rater or a qualified individual not involved in the treatment of the patients who has been instructed in the appropriate administration of the test. Patients are presented with a test instrument at the top of which there is a row of nine numbers paired with unique symbols. Below this part of the test instrument is an array of symbols paired with empty spaces, the patient's task is to verbally match the number for each symbol as quickly as possible. The test takes approximately 5 minutes to administer. The test scoring is calculated based on the number of correct answers in 90 seconds.

#### Low Contrast Visual Acuity (LCVA):

The LCVA will be assessed according to the schedule in Appendix-1. Disturbances in visual function are common in patients with MS but these impairments are often not readily apparent on commonly used high- contrast acuity tests. The use of low-contrast visual acuity charts have therefore gained validity in the assessment of visual acuity in patients with MS. Low contrast Sloan letter charts provide a practical, quantitative, and standardized assessment of visual function. Each chart consists of rows of gray letters, decreasing in size from the top to the bottom row, on a white background. A complete set consists of 7 charts, each with a different level of contrast ranging from 100% (normal vision chart) to 0.6%. For this study only two charts will be used, the 100% (normal vision chart) and 2.5% contrast charts. When these charts are being rated it is important that standardized conditions are used (e.g. distance from the chart, lighting conditions). Letter scores indicate the number of letters identified correctly, each chart is scored

separately. Low-contrast letter acuity testing with Sloan charts is easy to administer and has been shown to have high inter-rater reliability both in patients with MS and in healthy volunteers.

### **Magnetic Resonance Imaging (MRI)**

A baseline MRI scan of the central nervous system (CNS) will be obtained. Both T1 and T2-weighted images will be obtained.

The following parameters will be assessed using these MRI data:

- Myelin water fraction
- Magnetization Transfer Ratio
- Radial diffusivity on Diffusion Tensor Imaging
- Number of new/enlarging T2 hyperintense lesions
- Total volume of T2 lesions,
- Volume of un-enhancing T1 hypointense lesions,
- Change in brain volume

All images will be obtained on the NIC MS Scanner in the Sandler Neurosciences Building. All scans will be performed by a trained MRI technician using protocols previously defined within the lab (specific MR settings to be defined elsewhere). Each MRI scan performed for the study, both scheduled and unscheduled (e.g. ordered by the investigator for safety or differential diagnosis), will be reviewed by a neuroradiologist. The Primary Treating Physician must be contacted in case of unexpected findings (not consistent with MS) detected on the MRI scan for safety actions and Adverse Event reporting. During the study each scan performed, both scheduled and unscheduled, will be assessed by the blinded trained physician from the NIC MS MRI team. Upon acquisition the MRI will be evaluated for quality, completeness, and adherence to the manual. Confirmation of MRI quality or a description of the quality problems, if detected, will be communicated to the investigators. If scan is incomplete or incorrectly performed, the study center will be asked to repeat it as soon as possible. After completion of the quality check, all scans will be analyzed according to a standardized procedure.

For the MRI exam, each participant will be asked a number of questions concerning his or health, lack of metal implants and absence of claustrophobia. They will be asked to lie down on a narrow bed that will then be moved into a tunnel that is 6 feet by 2.5 feet. Each person will need to lie there quietly for about 1.5 hours during which time machine-like banging noises will occur. Earplugs will be provided to reduce the sound level. Communication with the technologists outside will be possible at all times by a microphone and loudspeaker. If the participant wishes to be removed from the magnet, this will be done immediately.

### **Visual Assessments**

A routine functional visual assessment will be made. The investigator will examine the volunteer's eyes (visual acuity, pupil exam, color, motility, King Devick's test for saccades, dilating exam, intraocular pressure). The patient may be asked to fill out a questionnaire regarding their visual function. Then an OCT will be performed. Ocular Coherence Tomography (OCT) is a special test that evaluates and counts the retinal fiber layer by having the participant focus on a target.

The entire examination will last approximately one hour and 15 minutes (seventy-five minutes) -- some patients will additionally be offered special tests that include:

1. Full-Field visual evoked potential (ffVEP) and multifocal electroretinogram (ERG) are special tests that provide information about optic nerve function by having the participant focus on a constantly changing array of checkerboard lights.
2. Octopus 900 visual field analyzer using a Humphrey's protocol (HVF FDT) or Heidelberg Perimetery (HEP) visual field analyzer are special automated visual field tests that specifically evaluate ganglion cell function by having the participant push a button when they see a light.

This additional testing will require approximately two hours (one-hundred and twenty minutes).

### **Ophthalmologic Examination**

Patients will undergo screening ophthalmologic exam to include assessment for any undiagnosed ophthalmologic disease that could impact assessments including but not limited to dilated examination of the fundus and macula by study investigator. This evaluation will include an eye history, visual acuity measurements and dilated ophthalmoscopy at the screening visit.

### **Pharmacokinetics/Lab Tests**

Participant's serum and PBMCs will be properly stored for later analysis (if needed).

#### **9.1.7 Adverse Events**

Information regarding occurrence of adverse events will be captured throughout the study. Duration (start and stop dates and times), severity/grade, outcome, treatment and relation to study drug will be recorded on the case report form (CRF).

### **9.2 Clinical Laboratory Measurements**

#### **9.2.1 Hematology**

Blood will be obtained and sent to each site's clinical hematology lab for a complete blood count (hemoglobin, hematocrit, red blood cell count, white blood cell count, white blood cell differential, and platelet count), and serum C-reactive protein (CRP) determinations for assessment of systemic evidence for infection and/or inflammation.

#### **9.2.2 Blood Chemistry Profile**

Blood will be obtained and sent to each site's clinical chemistry lab for determination of serum sodium, potassium, chloride, bicarbonate, random glucose, BUN, creatinine, aspartate aminotransferase (AST/SGOT), alanine aminotransferase (ALT/SGPT), alkaline phosphatase, total bilirubin, direct bilirubin.

## **10 EVALUATIONS BY VISIT**

### **10.1 Visit 1 (Week 0) - Screening**

1. Review the study with the subject and obtain written informed consent and HIPAA authorization and assent, if appropriate.
2. Assign the subject a unique screening number.

3. Record demographics data.
4. Record medical history, including a history of MS, diagnosis date, and prior MS treatments, as well as history of optic neuritis.
5. Record concomitant medications.
6. Perform a complete physical examination.
7. Perform VEP and OCT assessments (if no record of assessment within past 6 months)
8. Perform and record vital signs.
9. Perform and record results of blood pressure testing.
10. Collect blood for clinical laboratory tests (chemistry, hematology, pregnancy test)
11. Initiate subject diary
12. Schedule subject for Visit 2 in 14 days +/-2.

### 10.2 Visit 2 (Baseline)

1. Concomitant medications review.
2. Perform abbreviated physical examination.
3. Assess likely side effects via clinician observation and questionnaires
4. Perform and record vital signs.
5. Perform neurologic & ophthalmologic exam.
6. Perform and record visual assessments (OCT, high/low contrast vision testing, cone contrast, VFQ)
7. Perform and record cognitive & other tests (SDMT, MFIS, EDSS, SF-36)
8. Perform timed walking tests (T25W, TUG, 6min walking test)
9. Perform MRI (no contrast)
10. Randomize subject, dispense study drug
11. Collect blood for research laboratory tests (if needed)

### 10.3 Visit 3 (3-month)

1. Record any Adverse Experiences and/or Review subject diary for adverse experiences and dosing compliance.
2. Record changes to concomitant medications.
3. Perform abbreviated physical examination.
4. Assess likely side effects via clinician observation and questionnaires
5. Perform and record vital signs.
6. Collect blood for research laboratory tests (if needed)
7. Perform neurologic and ophthalmologic exam.
8. Perform and record visual assessments (high/low contrast vision testing, cone contrast, VFQ)

9. Perform and record cognitive & other tests (SDMT, MFIS, EDSS, SF-36)
10. Perform timed walking tests (T25W, TUG, 6 min walking test)
11. Perform MRI (no contrast)

#### **10.4 Visit 4 (6-month)**

1. Record any Adverse Experiences and/or Review subject diary for adverse experiences and dosing compliance.
2. Record changes to concomitant medications.
3. Perform abbreviated physical examination.
4. Assess likely side effects via clinician observation and questionnaires
5. Perform and record vital signs.
6. Collect blood for research laboratory tests (if needed)
7. Perform neurologic and ophthalmologic exam
8. Perform and record visual assessments (OCT, high/low contrast vision testing, cone contrast, VFQ)
9. Perform and record cognitive & other tests (SDMT, MFIS, EDSS, SF-36)
10. Perform timed walking tests (T25W, TUG, 6 min walking test)
11. Perform MRI (no contrast)
12. Collect blood for clinical laboratory tests (chemistry, hematology)

#### **10.5 Early Withdrawal Visit**

1. Record any Adverse Experiences and/or Review subject diary for adverse experiences and exclusionary medication use.
2. Record changes to concomitant medications.
3. Perform complete physical examination.
4. Perform and record vital signs.
5. Collect blood for clinical laboratory tests (chemistry, hematology)

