#### 3.2 Secondary Objectives

- The first key secondary objective is to assess whether latency delay at 180 days decreases to a greater extent in Group A (exposed to BZA for 90 days during both Stage 1 and Stage 2) when compared to Group B (exposed to placebo during Stage 1 and BZA for only 90 days during Stage 2).
- The second key secondary objective is to demonstrate the tolerability of BZA in this population. This will include special focus with regards to fatigue as this is a major symptom for patients suffering from multiple sclerosis.
- The third key secondary objective is to document the safety of BZA in this population of patients.
- The fourth key secondary objective of this study is to help assess which secondary and tertiary outcomes are likely to be informative for future remyelinating trials in multiple sclerosis.

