#### **5.3.5 Fatigue Assessment**

To ensure patient safety in daily activities, we will conduct a fatigue assessment at each of the visits indicated in Appendix-1, in order to monitor the degree of self-reported fatigue experienced.

The Modified Fatigue Impact Scale (MFIS) is a 21-item fatigue scale that measures the physical, cognitive, and psychosocial aspects of fatigue.

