## **12 DISCONTINUATION AND REPLACEMENT OF SUBJECTS**

### **12.1 Early Discontinuation of Study Drug**

A subject may be discontinued from study treatment at any time if the subject, the investigator, or the Sponsor feels that it is not in the subject's best interest to continue. The following is a list of possible reasons for study treatment discontinuation:

- Subject withdrawal of consent (or assent)
- Subject is not compliant with study procedures
- Adverse event that in the opinion of the investigator would be in the best interest of the subject to discontinue study treatment
- Protocol violation requiring discontinuation of study treatment
- Lost to follow-up
- Sponsor request for early termination of study
- Positive pregnancy test (females)

If a subject is withdrawn from treatment due to an adverse event, the subject will be followed and treated by the Investigator until the abnormal parameter or symptom has resolved or stabilized.

All subjects who discontinue study treatment should come in for an early discontinuation visit as soon as possible and then should be encouraged to complete all remaining scheduled visits and procedures.

All subjects are free to withdraw from participation at any time, for any reason, specified or unspecified, and without prejudice.

Reasonable attempts will be made by the investigator to provide a reason for subject withdrawals. The reason for the subject's withdrawal from the study will be specified in the subject's source documents. Refer to Section 10 for early termination procedures.

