#### APPENDIX 1. SCHEDULE OF STUDY VISITS

	SCREENING VISIT 1 (Screen) a	STUDY1 VISIT 2 (Baseline) a	STUDY2 VISIT 3 (Month 3) a	STUDY3 VISIT 4 (MONTH 6)
Informed Consent	X			
Medical History	X			
Complete Physical Exam	X			
Abbreviated Physical Exam		X	X	X
Height	X			
Weight	X			
Vital Signs	X	X	X	X
Pregnancy Test (Serum)	X			
Hematology	X		X	X
Chemistry	X			X
Research blood stored	X	X	X	X
Neurological + ophthalmological exam with neurologist		X	X	X

MRI		X	X	X
Randomization	X			
Dispensing of Study Drug		X	X	
Counting of Returned Study Drug				X
Initiate Subject Diary	X			
Subject Diary Review		X	X	X
Concomitant Medication Review	X	X	X	X
Additional cognitive assessments		X	X	X
OCT	X	X		X
VEP	X	X	X	X
Vision testing (high, low contrast)		X	X	X
Cone contrast		X	X	X
VFQ		X	X	X
Questionnaires (MFIS, MSWS12, SF-36)		X	X	X
Assess likely side effects		X	X	X
EDSS		X	X	X
SDMT		X	X	X
Timed walking tests		X	X	X
ERG** (optional)	X			

Safety phone call at Week 6.

\*\* \*\*In rare cases during the initial visit, the patient may be asked to undergo an electroretinogram. This test measures the electrical response of the eye's light-sensitive cells, called rods and cones. These cells are part of the retina (the back part of the eye). This test is used to detect disorders of the retina. For this study, this option exists only to be used in cases where more information is needed to confirm a diagnosis of optic neuritis. The test is performed by placing numbing drops in the patient's eyes, so that there is no discomfort. Then, the patient's eyes are held open with a small device called a retractor. An electrical sensor (electrode) is placed on each eye and the electrical activity of the retina is recorded in response to light. The primary risk associated with the study is a temporary scratch of the surface of the cornea due to the electrode. Otherwise, there are no risks associated with this procedure.

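### The Early Withdrawal Visit schedules neither the fatigue scale nor the side-effect assessment, so fatigue scores may be selectively missing, or taken only off drug, in patients who stop during Stage 1

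*Combined protocol and SAP*

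**What the plan says.** Section 3.2 states: "The second key secondary objective is to demonstrate the tolerability of BZA in this population". It adds: "This will include special focus with regards to fatigue as this is a major symptom for patients suffering from multiple sclerosis". The instrument is given in Section 5.3.5: "The Modified Fatigue Impact Scale (MFIS) is a 21-item fatigue scale that measures the physical, cognitive, and psychosocial aspects of fatigue". That section ties the fatigue assessment to the visits marked in Appendix 1.

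Sections 10.2, 10.3 and 10.4 (baseline, Month 3, Month 6) each list the MFIS, and each includes the item "Assess likely side effects via clinician observation and questionnaires". Appendix 1 agrees: the row beginning "Questionnaires (MFIS, MSWS12, SF-36" is marked at these three visits and nowhere else.

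For a patient who stops treatment, Section 12.1 says: "All subjects who discontinue study treatment should come in for an early discontinuation visit as soon as possible". It then asks that she be encouraged to attend the remaining visits, and refers to Section 10 for the procedures. Section 10.5 has five items:

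- adverse experiences and diary ("Record any Adverse Experiences and/or Review subject diary for adverse experiences and exclusionary medication use")
- changes in concomitant medication
- a full physical examination
- vital signs
- blood for chemistry and hematology

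Appendix 1 has four columns (screening, baseline, Month 3, Month 6) and none for early withdrawal.

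**The concern.** Fatigue is the one symptom that the tolerability objective names, and the MFIS is the only scale given for it. A patient who finds the drug hard to tolerate is more likely than others to stop. The visit held when she stops does not score her fatigue.

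Stage 1 is the only placebo-controlled period. If the most fatigued patients on BZA have no Stage 1 score, or only one taken after the drug was withdrawn, the Stage 1 MFIS summary leans toward the conclusion that BZA is well tolerated. A score not taken at the time of stopping cannot be recovered later.

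**Working it through.** The check is mainly a comparison of visit lists. The plan states no figure for fatigue, tolerability or early withdrawal, so there is nothing to reproduce.

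**Which MFIS scores the plan yields after baseline**

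| Patient | Provision | MFIS obtained |
|---|---|---|
| Stays on treatment to Month 3 | Section 10.3 | Stage 1 score, on treatment |
| Stops drug in Stage 1, returns for Visit 3 | Section 10.5, then encouragement in 12.1 | Stage 1 score, off drug for up to about 3 months |
| Leaves the study in Stage 1 | Section 10.5 only | None scheduled |
| Leaves between Visits 3 and 4 | Section 12.2: encouraged to attend a final visit with the next visit's procedures | Stage 1 score exists; a Stage 2 score if she attends |

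The rule in Section 12.2 that brings in the next visit's procedures covers only withdrawal after Visit 3. Stage 1 has no equivalent. A Group B patient who leaves after Visit 3 and does not attend the final visit has no MFIS on BZA.

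**Direction and form of the effect**

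Let 25 be the number per group (Section 15.6) and k the number in an arm with no Stage 1 score. Let D be their mean worsening minus that of the patients who are scored. The mean over all 25 equals the mean of those scored plus (k/25) × D, so the observed mean understates worsening by (k/25) × D. For the comparison between arms the shift is

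(k_A/25) × D_A − (k_B/25) × D_B.

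Patients who stop placebo count too, and with equal numbers and equal D the shift is zero.

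**Illustration with assumed inputs.** The documents give neither k nor D. In SD units of MFIS change, for D from 0.5 to 1.5, one arm's mean shifts by:

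- k = 1: 1/25 × 0.5 = 0.02 to 1/25 × 1.5 = 0.06
- k = 2: 0.04 to 0.12
- k = 3: 0.06 to 0.18
- k = 5: 0.10 to 0.30

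With three missing on BZA, one on placebo and D = 1 in both arms, the between-arm shift is 0.12 − 0.04 = 0.08 SD. These figures show only how the effect scales.

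For patients who stop and return, the corresponding shift is (k/25) × (score at stopping − Month 3 score). It is zero if fatigue does not change after stopping. It counts as bias only if the question is tolerability while taking the drug.

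**The case against.** The strongest reply is that a patient who stops for fatigue is still counted. Section 10.5 records adverse experiences and reviews the diary at this very visit. Section 11.1 requires the investigator to ask about adverse events at each visit and to record severity and relation to drug. Side effects are sought by telephone at Week 6 and analyzed (Section 15.5). Section 14 requires the reasons for stopping to be recorded. The Safety Population needs only one dose (Section 15.1), and adverse events are tabulated by group (Section 15.4). All of this stands. A reader might infer that tolerability is measured only in patients who tolerate BZA; these provisions show that it is not. They do not, however, yield a fatigue score. Where fatigue is already common at baseline, worsening is better shown by change on the scale than by the presence of an event.

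Second, Section 14 lists the MFIS among safety assessments made throughout patient visits, and it requires a Safety Follow-Up visit of anyone who stops medication. This may show an intention to score fatigue. But the list names no visit, and the content of the follow-up visit is not defined. The specific list in Section 10.5 and the schedule in Appendix 1 do not carry the intention out.

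Third, no test of MFIS means is planned: the scale sits under safety evaluations and tolerability is to be summarized by group. This limits the consequence to a descriptive summary, though one that serves a key secondary objective.

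Fourth, keeping a Month 3 score from a patient who has stopped drug fits the all-randomized approach of Section 15.3. That is correct. Replacing it with an earlier score would be a debatable choice of estimand, and the early visit has no set interval after the last dose, so its score is not certain to be on drug either.

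Fifth, Section 1.2 reports that in an earlier two-year trial adverse-event incidence with BZA did not differ significantly from placebo. Differential stopping may thus be small, but that statement gives no fatigue scores.

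**Conclusion.** The gap is real and modest. Followed as written, the plan schedules no post-baseline MFIS for a patient who leaves the study during Stage 1, and only an off-drug MFIS for one who stops drug and returns at Month 3. If those who stop are the more fatigued, and more of them are on BZA, the Stage 1 MFIS summary favours BZA. Both conditions are plausible but are assumptions. The documents do not allow the size to be estimated, and no sample-size, power or alpha figure is affected.

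A reader might also infer that such missingness is beyond any analysis. That goes too far. Section 15.3 names no method for loss to follow-up, but a detailed SAP is still to be written, and sensitivity analyses that shift the missing scores by a range of amounts could be specified there. They would rest on untestable assumptions, which is why collecting the score is better.

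**What to change.** - Add to Section 10.5, and to a new early-discontinuation column in Appendix 1: the MFIS, the side-effect assessment already used at Visits 2 to 4, and the date of last dose. The date shows how close to treatment the score was taken.
- Reconcile Section 10.5 with the safety list in Section 14. State what the Safety Follow-Up visit contains and whether it is the same visit.
- In the SAP, keep observed Month 3 MFIS values in the all-randomized summary. Use the early-visit score where no later Stage 1 score exists. Report the MFIS at discontinuation by arm as a supportive on-treatment summary.

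The cost is a few minutes at a visit that already takes place, one schedule column and a short paragraph in the SAP. The drawback is that early-visit scores come from different days, after differing exposure, so the summary should state the timing.
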